#### **3.2 Secondary Hypotheses**

The secondary hypotheses are:

- Subjects treated with pamidronate will have higher total body BMC (TBMC; excluding head; adjusted for height, age, sex, Tanner stage, and race) measured by DXA 1 year post-HCT compared to the Control Group.
- Subjects treated with pamidronate will have higher total BMD, cortical BMD, trabecular BMD, and estimated bone strength measured by peripheral quantitative computed tomography (pQCT) 1 year post-HCT compared to the Control Group.
- Cytokine levels will increase rapidly in the first 3 weeks after HCT, preceding an increase in markers of bone resorption.
- In the Control Group, increased cytokine levels and receptor activator of nuclear factor- $\kappa$  B ligand (RANKL)/osteoprogenin (OPG) ratio 3 weeks post-HCT will be associated with decreased BMC and BMD 1 year after HCT.
- Markers of bone resorption will increase in the first 3 months after HCT, will remain elevated until at least Day 180 in the Control Group, but will decrease after initiation of pamidronate at Day 90 in the Pamidronate Group.
- Markers of bone formation, including osteocalcin (OCN), will decrease in the first 3 months after HCT and in the Control Group lower OCN levels at Day 90 will be associated with lower BMC and BMD 1 year post-HCT.

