## 8 Study Related Tests and Procedures

### 8.1 Schedule of Tests and Procedures

	Screen a	Study Entry b	Day 0	Day 7 (±2)	Day 14 (+ 2)	Day 21 (±2)	Day 90 (±14)	Day 180 (±14)	Day 270 (±30)	Day 360 (±30)
Informed Consent / Assent	X or X									
Physical Examination	X c or X c									X c
Weight	X	X					X	X	X	X
Height		X								X
Medical History	X or X						X	X	X	X
Medication Usage	X or X					X	X	X	X	X
Creatinine	X or X						X	X	X	
Urine or serum Pregnancy Test d,e	X or X						X	X f	X f	X
Diet & Activity Questionnaire		X					X	X	X	X
Adverse Event Assessment							X	X	X	X
Ionized/ or corrected Calcium	X or X						X f	X f	X f	
Vitamin D (D 2 +D 3 )	X or X						X g	X	X	X
iPTH		X					X			X
CTX, P1NP, & OCN		X		X	X	X	X	X		X
Urinary DPD and Creatinine		X		X	X	X	X	X		X
RANKL & OPG		X		X	X	X	X			
IL-6, IL-7, & TNF- $\alpha$		X		X	X	X	X			
DXA h		X					X			X
pQCT i							X			X
HCT			X							
Vitamin D & Calcium Administration j			X-----							X
Randomization – refer to section 6.2							X			
Pamidronate Administration k							X	X	X	
End of infusion (same day) serum calcium							X l	X l	X l	
Post infusion (next a.m.) m serum creatinine and spot urine for albumin and creatinine							X l	X l	X l	
Adverse event assessment by telephone 1 week post infusion (+/-3 days)							X l	X l	X l	

CTX = carboxy-terminal collagen crosslinks; DXA = dual-energy x-ray absorptiometry; DPD = deoxypyridinoline; HCT = hematopoietic cell transplantation; IL = interleukin; iPTH = intact parathyroid hormone; OCN = osteocalcin; OPG =

osteoprotegerin; P1NP = procollagen type 1 amino-terminal propeptide; pQCT = peripheral quantitative computed tomography; RANKL = receptor activator of nuclear factor- $\kappa$  B ligand; TNF- $\alpha$  = tumor necrosis factor alpha.

a Screening will occur during the pre-HCT work-up.

b Evaluations and tests only in the Study entry column are performed only after consent is signed and must be completed within 4 weeks (6 weeks for DEXA) prior to beginning pre-HCT conditioning regimen. If DEXA cannot be completed prior to conditioning, this will not be considered a protocol deviation

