## 12.4 Statistical Methods

The primary analysis will compare the Pamidronate and Control groups according to LBMC measured by DXA using all available Day 360 measurements and adjusting for height, age, sex, Tanner score, and race. The analysis will be a multiple linear regression; the primary predictor will be randomized treatment assignment and adjusters listed above. If preliminary analysis shows that LBMC measurements have a grossly non-Gaussian (non- normal) distribution, a transformation of LBMC will be analyzed, most likely  $\log_{10}$  LBMC Secondary analyses will include the following:

- The hypothesis that subjects randomized to pamidronate will have higher total BMD, cortical BMD, trabecular BMD, and estimated bone strength measured by pQCT at 1 year compared to subjects randomized to control (Aim 1 Hypothesis 2) will be tested by applying the foregoing analyses to outcomes measured by pQCT, namely bone strength, total BMD, cortical BMD, and trabecular BMD, but excluding height from the adjusters.
- The hypothesis that cytokine levels will increase rapidly in the first 3 weeks after HCT, preceding an increase in markers of bone resorption (Aim 2 Hypothesis 1) will be tested, for each cytokine, by using all available data for each child (up to 4 measurements from Day -14 to Day 21) and fitting a mixed linear model with a random intercept and time trend for each child and testing whether the average time trend differs from zero.
- The hypothesis that in the Control Group, increased cytokine levels and receptor activator of nuclear factor- $\kappa$ B ligand/osteoprotegerin ratio at 3 weeks will be associated with decreased BMC and BMD at 1 year after HCT (Aim 2 Hypothesis 2) will be tested using linear regressions with dependent variables being each of the BMC and BMD measures at Day 360 and predictors being changes in each of the cytokine levels and RANKL/OPG ratio (from Day -14 to Day 21).
- For the hypothesis that markers of bone resorption will increase in the first 3 months after HCT, will remain elevated until at least Day 180 in the

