Control Group, but will decrease after initiation of pamidronate at Day 90 (Aim 3 Hypothesis 1), the test of changes up to Day 90 will use the same type of analysis as for Aim 2 Hypothesis 1 but with up to 5 measurements (Day -14 to Day 90). Tests of changes after Day 90 will include all available data for each subject and use a mixed linear model to account for correlation of measurements within subject; changes over time will be tested separately in the Pamidronate and Control groups using contrasts and compared between groups by testing the interaction of group and measurement time (i.e., Day 180, Day 360).

For the hypothesis that markers of bone formation, including osteocalcin (OCN) will decrease in the first three months and in the Control Group lower OCN levels at Day 90 will be associated with lower BMC and BMD 1 year post-HCT (Aim 3 Hypothesis 2), the test of change in OCN to Day 90 will use all available data and the same type of analysis as for Aim 2 Hypothesis 1; the test of change from Day 90 to Day 360 will use control subjects only and simple linear regression with outcome each of the BMC and BMD measures at Day 360 and predictor OCN level at Day 90.

For analyses of Aims 2 and 3 and Aim 1 hypothesis 2, further secondary analyses will use multiple imputation to impute missing measurements. Finally, exploratory analyses will explore risk factors for bone loss, including sex, BMI percentile, LBM adjusted for height, calcium and vitamin D intake, CNS radiation, TBI vs. no TBI in conditioning regimen, donor stem cell source (cord blood vs. other), physical activity, and glucocorticoid exposure for prophylaxis or treatment of GVHD. Subjects who experience a bone fracture after HCT will be excluded from analyses of bone turnover markers but otherwise will be included in all analyses.

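### The test for Aim 2 Hypothesis 1 cannot show that cytokines rise before resorption markers, and its single time trend can miss an early surge that has faded by Day 21

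*Combined protocol and SAP*

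**What the plan says.** Section 3.2 states the hypothesis: "Cytokine levels will increase rapidly in the first 3 weeks after HCT, preceding an increase in markers of bone resorption". Section 12.4 repeats it as Aim 2 Hypothesis 1 and says it will be tested, cytokine by cytokine, by "fitting a mixed linear model with a random intercept and time trend for each child". What is then assessed is a single parameter; the plan describes this step as "testing whether the average time trend differs from zero". Each child contributes "up to 4 measurements from Day -14 to Day 21".

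Resorption markers appear under a different hypothesis. For Aim 3 Hypothesis 1 the plan says that "the test of changes up to Day 90 will use the same type of analysis as for Aim 2 Hypothesis 1", with a fifth measurement at Day 90. The only further analysis that Section 12.4 names for Aim 2 is multiple imputation of missing values.

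The schedule in Section 8.1 draws IL-6, IL-7 and TNF-α at Study Entry and Days 7, 14, 21 and 90. CTX and urinary DPD are drawn at those same visits, and again at Days 180 and 360. The Day -14 sample is nominal: tests listed only under Study Entry "must be completed within 4 weeks (6 weeks for DEXA) prior to beginning pre-HCT conditioning regimen".

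**The concern.** The hypothesis claims two things, and the test addresses neither directly.

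- **Order.** A claim that one quantity rises before another needs both quantities in the analysis. This test uses one. A significant cytokine trend, reported under the hypothesis as worded, would lend apparent support to a sequence that was not examined.
- **Speed.** One average trend from before transplant to Day 21 summarises the whole window. A surge that peaks early and subsides can leave that trend near zero, so a real response could be reported as no change. A slow, even rise also rejects, so a positive result does not show that the rise was rapid.

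**Working it through.** The plan gives no power, effect size or alpha for this hypothesis, so there is no figure of its own to reproduce.

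**Order.** Set side by side:
- Aim 2 Hypothesis 1: cytokines only, Study Entry to Day 21.
- Aim 3 Hypothesis 1, first part: resorption markers only, Study Entry to Day 90.

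Two separate trends over different windows can both be positive whichever rise came first. A simulation with 96 children and 4,000 runs per scenario shows this. The cytokine test rejected in 93–94% of runs whether the marker rose after, with or before the cytokine, or never rose.

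**Weights in the slope.** With complete data at common times, the average slope in a model with a random intercept and slope equals the mean of the per-child least-squares slopes. Its expected value is Σ(tᵢ − t̄)μᵢ / Sxx.
- Times −14, 7, 14, 21; t̄ = 28/4 = 7.
- Deviations −21, 0, +7, +14; Sxx = 441 + 0 + 49 + 196 = 686.

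Day 7 therefore has zero weight. A peak at Day 7 alone, of any height, gives an expected slope of zero. This rests only on the nominal days and the straight-line reading.

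**Power.** Assumptions: 90 children with complete data (96 are planned through Day 21), SD 1, equal within-child correlation 0.5, two-sided 5%.
- Slope test: standard error = √(0.5/686)/√90 = 0.00285; noncentral t with 89 df.
- Visit as a factor: Hotelling test on the three changes from Entry; noncentrality 90·Σ(μᵢ − μ̄)²/0.5; F with 3 and 87 df.

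For changes of +0.6, +0.3, 0, the slope is 7(0.3)/686 = 0.00306. Dividing by 0.00285 gives about 1.08, hence 19% power. For the visit test, Σ(μᵢ − μ̄)² = 0.2475, so the noncentrality is 44.6 and power is about 100%. For +0.5, +0.2, −0.1, the slope numerator is 7(0.2) − 14(0.1) = 0, so power is 5%.

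| Mean change from Entry at Days 7, 14, 21 (SD) | Slope test | Visit as a factor |
|---|---|---|
| +0.5, +0.2, −0.1 | 5% | about 100% |
| +0.6, +0.3, 0 | 19% | about 100% |
| +0.6, +0.5, +0.4 | 99.6% | about 100% |
| +0.4 throughout | 99% | 98% |
| even rise to +0.4 | 98% | 92–93% |
| even rise to +0.3 | 85% | 69% |
| even rise to +0.25 | 70% | 52% |

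**Timing of the first sample.** If every child's first sample fell on Day −7, the deviations would be −15.75, −1.75, +5.25, +12.25 (Sxx 428.75). On Day −28 they would be −31.5, +3.5, +10.5, +17.5 (Sxx 1,421). Day 7 keeps the smallest weight in both. By the same formula, slope-test power for +0.6, +0.3, 0 is 6% and 46% respectively. The loss therefore depends on when the first sample is taken, but does not disappear in this range.

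**The case against.** **The failure needs a particular profile.** Aim 2 Hypothesis 2 uses the cytokine change from Day -14 to Day 21 as a predictor, so the authors appear to expect levels still raised at Day 21. For such profiles the slope test works, even when the surge has partly faded (99.6% for +0.6, +0.5, +0.4). The low-power cases need a return to Entry level or slightly below by Day 21. The documents give no cytokine means, SDs or shapes. This stands, and it limits the point to transient surges.

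**Replacing the slope is not free.** This also stands. At 90 children, a three-degree-of-freedom joint test loses about 5 points if the rise is even to +0.4 SD, 16 points at +0.3 and 18 points at +0.25. It is also non-directional. A reader might infer that the slope test should be discarded; these figures do not support that.

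**Reuse for bone markers.** With Day 90 added, that visit dominates the slope. A reader might infer that this is a second fault. The documents do not support it: Aim 3 Hypothesis 1 concerns a rise over the first three months that persists, and a contrast led by Day 90 suits it.

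**Straight-line form.** Section 12.4 says time trend, not linear. A single average trend tested against zero, with no curve, change-point or visit factor named, is most naturally a line. If another form was meant, the plan should state it.

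**Importance.** The Study Summary lists this as a correlative objective. Neither the lumbar bone mineral content analysis nor safety monitoring depends on it.

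None of these supplies a test of order.

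**Conclusion.** The point holds on order without any numerical assumption: nothing in Section 12.4 compares the timing of the cytokine and marker rises, so the plan cannot support that half of its hypothesis.

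On speed it holds more narrowly. Under the straight-line reading at nominal days, a surge that has gone by Day 21 is detected with 5% to 19% power in the two assumed profiles, against about 100% with visit as a factor. A rise still present at Day 21 is detected well. Rejection shows an average change over the window, not a rapid one. The zero weight on Day 7 follows from the schedule; the power figures rest on assumed profiles, 90 children, correlation 0.5 and complete data.

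This should be corrected because it changes what the trial may conclude about mechanism. It does not touch the primary result.

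**What to change.** 1. **Order.** Specify a timing analysis using the CTX and DPD samples already scheduled at Study Entry and Days 7, 14, 21 and 90. One option is to estimate visit-specific changes from Entry for cytokines and markers on a standardised scale, and name in advance the comparison of early cytokine change with early marker change that would count as support. A regression of a marker on the previous visit's cytokine shows lagged association, not which rise came first, so it should not carry the claim alone. State which children contribute: Section 7.1 keeps those with vitamin D below 20 ng/mL at Study Entry out of the marker analyses until levels normalise, and Section 12.4 excludes children with a fracture after transplant. Otherwise, remove the claim of precedence from the Study Summary, Section 3.2, Section 12.4 and the eventual conclusion.
2. **Speed.** Keep the trend test and state its form and time scale. Add contrasts from Entry at Days 7, 14 and 21, with direction, from a model with visit as a factor. Section 12.4 already uses contrasts and a group-by-measurement-time interaction after Day 90, so this fits the plan's own methods.

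The cost is plan wording, slightly more analysis and a few more contrasts to report. No extra samples or visits are needed. Sampling is about weekly to Day 21 and then jumps to Day 90, so order can be resolved only to that grid; the report should say so.

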### **8.2.3 Medical Examination and Anthropometrics**

A physical examination will be performed by a trained pediatric provider at study screen/entry and at the day 360 visit per section 8.1. Height will be recorded at study entry and on day 360. Weight will be recorded at study screening/entry and on days 90, 180, 270 and 360. Tanner staging of pubertal development, including breast and pubic hair development in girls (52), and pubic hair development in boys (53) will be performed at each physical exam. Height will be measured standing without shoes with a wall-mounted stadiometer. Weight will be measured with subject in light clothing or dressing gown with shoes removed. These measurements will be used to calculate BMI as weight (kg) divided by height (m^2).

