#### Laboratory Reference Ranges

	University of Minnesota (UMN)		Fred Hutchinson Cancer		
Creatinine (mg/dL)	0-21d	0.33-1.01	2 months-2 years	0.1-0.4	
	22 days-8 years	0.15-0.53			
	9-14 years	0.39-0.73		0.1-0.6	
	15-19y	0.5-1.0		0.2-0.9	
	20 y and older, F	0.52-1.04		0.2-1.1	
Calcium ("corrected calcium"?)	20 y and older, M	0.66-1.25	≥14 years	8.7-10.7	
	Age	mg/dL			
	0-11 mo	8.5-10.7			
	1-18 yr	9.1-10.3			
	19 yr & older	8.5-10.1			
Ionized Calcium	Age	mg/dL			
	0-11 mo	5.1-6.3			
	1 yr and older	4.4-5.2			
Vit D (D2 + D3) / 25-hydroxy (OH) vitamin D (ng/mL)	20-75		30-100		
Intact parathyroid hormone (iPTH) (pg/mL)	12-72pg/mL		12-75		
Interleukin (IL)-6 (pg/mL)	≤3.0		≤3.0		
IL-7 (pg/mL)	0.66-9.2		0.66-9.2		
Tumor necrosis factor alpha (TNF- $\alpha$ ) (pg/mL)	≤8.8		≤8.8		

a IL-6, IL-7, and TNF- $\alpha$  samples from Fred Hutchinson Cancer Research Center will be analyzed at UMN.

Laboratory normal ranges for CTX, DPD, P1NP, OCN, RANKL, and OPG vary with age. Urinary DPD will be adjusted for urinary creatinine content.

If total calcium or vitamin D (D2+D3)/25-OH vitamin D is below the normal range, supplementation will be administered per Section 7.3.

If creatinine level for a subject randomized to receive pamidronate becomes elevated during the study (creatinine level  $>2$  times the baseline value at Study Entry) refer to section 7.3.2 for treatment modification and monitoring.

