## **11 Endpoints**

### **11.1 Primary Clinical Endpoint**

The primary endpoint is Lumbar BMC measured by DXA at 1 year after HCT (adjusted for height, age, sex, Tanner stage and race).

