### **11.2 Secondary Clinical Endpoints**

Other endpoints are:

- TBMC measured by DXA (adjusted for height, age, sex, Tanner stage and race).
- Estimated bone strength, total BMD, cortical BMD, and trabecular BMD of the left tibia and non-dominant radius measured by pQCT.
- Levels of markers of bone resorption (carboxy-terminal collagen crosslinks [CTX] and deoxypyridinoline [DPD]), and bone formation (procollagen type 1 N-terminal propeptide [P1NP] and OCN)
- RANKL, OPG, and RANKL/OPG ratio.
- Levels of cytokines including interleukin (IL)-6, IL-7, and tumor necrosis factor-alpha (TNF- $\alpha$ ).
- Body composition: body mass index (BMI) percentile, lean body mass, and body fat mass (from DXA) adjusted for height.

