## **12 Statistical Considerations**

### **12.1 Sample Size**

Sixty (60) subjects total (30 each in the Control and Pamidronate groups) gives 80% power to detect a difference between groups of 0.75 standard deviations (SDs)

describing variation in LBMC within study group after adjusting for height, age, sex, Tanner score, and race. Adjusting for age and sex, this SD is 5-8g (46, 47); adjusting further for race and height should reduce this SD by about half (48-50). This gives a within-group SD of about 2.5-4g and a detectable difference of 2-3g. To have 60 evaluable subjects, 192 need to be screened to allow for a 50% consent rate, 10% death rate by Day 90, 20% death rate between Day 90 and Day 360, and 10% drop out after randomization.

Anticipated Enrollment Over Duration of Study

	Screen	Study Entry Day -14 a	Day 7	Day 14	Day 21	Day 90	Day 180	Day 270	Day 360
Total	192	96	96	96	96	86	86	86	60
University of Minnesota (UMN)	96	48	48	48	48	43	43	43	30
Fred Hutchinson Cancer Research Center	96	48	48	48	48	43	43	43	30
a Day 0 is the day of hematopoietic cell transplantation (HCT).									

According to data from 2011 to 2012, 36 allogeneic transplants have been performed at UMN and 37 have been performed at Fred Hutchinson Cancer Research Center. It is expected that screening 28 patients per year will be feasible for both sites.

It anticipated that enrollment will take 3.5 years.

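### The control-group test of Day 90 osteocalcin against Day 360 bone measures has no age or size term and leaves BMC undefined; separately, the fracture rule discards marker samples taken before the fracture

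*Combined protocol and SAP*

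**What the plan says.** **OCN test.** For Aim 3 Hypothesis 2, Section 12.4 specifies, in control subjects only, "simple linear regression with outcome each of the BMC and BMD measures at Day 360 and predictor OCN level at Day 90". No other predictor is named.

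**Meaning of BMC.** Section 11.1 describes the LBMC endpoint as "adjusted for height, age, sex, Tanner stage and race", and Section 11.2 attaches the same list to TBMC. Neither defines a Z-score, residual or other adjusted value. In the primary analysis the adjustment is made inside the model: "The analysis will be a multiple linear regression; the primary predictor will be randomized treatment assignment and adjusters listed above". The outcome of that regression is therefore the measured LBMC. For pQCT outcomes, Section 12.4 applies the same treatment comparison "but excluding height from the adjusters"; Section 11.2 attaches no adjustment to pQCT BMD.

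**Age and growth.** Section 5.1.2 admits ages 1 to 20. Section 8.3.5 states: "Laboratory normal ranges for CTX, DPD, P1NP, OCN, RANKL, and OPG vary with age". Section 12.1 states that "adjusting further for race and height should reduce this SD by about half", starting from an SD already adjusted for age and sex.

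**Covariate timing.** Section 8.2.3: "Height will be recorded at study entry and on day 360". Tanner stage is assessed at the physical examinations, at screening or entry and at Day 360.

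**Fracture rule.** The end of Section 12.4 excludes any subject with a fracture after HCT from turnover-marker analyses, with no time limit. By contrast, Section 7.1 excludes subjects with low vitamin D at entry from the same analyses only until the level normalises.

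**The concern.** The primary comparison is randomised, so growth is balanced on average, and it is nevertheless adjusted for five variables. The OCN test is observational, in subjects from toddlers to young adults, and nothing in it controls age or size. On measured BMC there are two ways to go wrong. If OCN tracks growth, a significant slope may be growth alone. If it does not, growth variance stays in the residual and can hide a real association. Two statisticians could also run different tests from the same text, because BMC can be read as measured or adjusted.

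The fracture rule is a separate matter. It deletes samples taken before the fracture, some of them before randomisation, and it selects subjects for the randomised group-by-time marker comparison on an event that may follow randomisation.

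**Working it through.** **Plan's own figures.** The documents state no alpha; I assume two-sided 5% throughout.
- Primary sample size: 2(1.96 + 0.842)²/0.75² = 27.9, so 28 per group by the normal approximation. With 30 per group the t-test power is 81.5%, against 80% stated.
- Detectable difference: 0.75 × 2.5 = 1.9 g to 0.75 × 4 = 3.0 g, against 2-3 g stated.

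No power is stated for the OCN regression.

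**How strongly the adjusters predict LBMC.** Halving the SD leaves (1/2)² = 1/4 of the age- and sex-adjusted variance. All adjusters together therefore have R² ≥ 0.75, or R ≥ √0.75 = 0.866.

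**Scenario A: measured BMC, OCN tracks growth, no OCN effect of its own.** The induced correlation is (OCN-growth r) × 0.866, for example 0.4 × 0.866 = 0.35. Simulated null rejection with n = 30 and 40,000 replicates:

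| Assumed OCN-growth r | OCN only | Five adjusters |
|---|---|---|
| 0 | 5% | 5% |
| 0.2 | 15% | 5% |
| 0.4 | 48% | 5% |

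**Scenario B: measured BMC, OCN unrelated to growth, assumed true partial correlation 0.5.** Without adjusters the residual SD doubles, so the crude correlation is about 0.25.
- Fisher z, OCN only: atanh(0.25) × √27 − 1.96 = −0.63, power 26%.
- Fisher z, five adjusters: atanh(0.5) × √22 − 1.96 = 0.62, power 73%.
- Simulation: 27% and 75%.

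**Scenario C: BMC already adjusted.** Null rejection is 3-5% and power 66-74%, so there is no inflation.

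**pQCT BMD.** pQCT is done at UMN only, so about 30/2 = 15 controls are expected. With an assumed outcome-age correlation of 0.3-0.5, null rejection without adjusters is 5-11%, and 5% with age and sex. Power at partial correlation 0.5 (OCN unrelated to age) is 38-46% unadjusted, 44% with age and sex, and 36-37% with four adjusters.

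**Timing of height and Tanner stage.** Suppose OCN correlates 0.4 with growth between Study Entry and Day 360, with no true effect (5,000 replicates). At assumed correlations of 0.95/0.97/0.99 between the entry and Day 360 growth composites, Study Entry adjusters reject 15/12/8% of the time. Day 360 adjusters reject about 5%.

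**Fracture rule.** Section 8.1 schedules seven CTX/P1NP/OCN samples (Study Entry, Days 7, 14, 21, 90, 180, 360). With 86 at Day 90, 86 × 7 = 602 before attrition. Five samples precede a fracture between Day 90 and Day 180, and six precede one between Day 180 and Day 360. The documents give no fracture rate.

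| Assumed rate | Subjects | Removed now (×7) | Recoverable (×5 to ×6) |
|---|---|---|---|
| 5% | 4 | 28 | 20-24 |
| 10% | 9 | 63 | 45-54 |
| 20% | 17 | 119 | 85-102 |

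Selection bias in the group comparison is 0 SD if pamidronate does not affect fracture. It is 0.012-0.070 SD for an odds ratio of 0.5, fracture rates of 5-20% and marker-liability correlations of 0.3-0.5, all assumed.

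**The case against.** The best defence is that Sections 11.1 and 11.2 already call LBMC and TBMC adjusted. Read that way, the gap is one of wording and the test is sound (scenario C). This stands as a possible reading, but it does not settle the matter: no adjusted score is defined, the only mechanism in the plan is covariates in a different regression, and pQCT BMD carries no adjustment at all here.

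The unfavourable figures also depend on inputs that the documents do not give: the OCN-growth correlation and the true partial correlation. Age-dependent normal ranges make a correlation plausible but fix neither its size nor its sign. That objection stands.

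A reader might infer more than the documents support:
- **Inflation and power loss together.** Scenario A needs OCN to track growth; the 27% against 75% contrast needs it not to.
- **A power gain for pQCT.** The figures show none to speak of; the case there is control of confounding.
- **A loss of 28, 63 or 119 samples that could be saved.** Those counts include post-fracture samples that a better rule would also drop.
- **A materially biased randomised marker comparison.** The bias is probably small and may be zero.

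Study Entry height and Tanner stage have one advantage: they precede the Day 90 predictor. As main covariates they leave interval growth uncontrolled, so they belong in a sensitivity analysis.

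**Conclusion.** The concern holds as a minor one, confined to correlative hypotheses. The OCN regression has no age or size term and an undefined BMC outcome. On measured BMC it is confounded to the extent that OCN tracks age or growth (null rejection 5/15/48% at assumed correlations 0/0.2/0.4), or it loses power if OCN does not (27% against 75% at an assumed partial correlation of 0.5). Neither follows if an adjusted BMC is meant.

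The fracture rule discards usable samples: at most about 20-24, 45-54 or 85-102 of 602 are recoverable at assumed rates of 5, 10 or 20%. Those figures take all fractures as falling after Day 90 and ignore attrition. The primary analysis is unaffected by either matter.

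**What to change.** In Section 12.4:

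1. **Aim 3 Hypothesis 2, BMC.** Replace the simple regression with a multiple regression of measured Day 360 BMC on Day 90 OCN plus the primary-analysis adjusters (height, age, sex, Tanner stage, race). Use Day 360 height and Tanner stage to match the outcome, and repeat with Study Entry values as a sensitivity analysis.
2. **Aim 3 Hypothesis 2, pQCT BMD.** Include at least age. State whether the treatment-comparison set without height is kept, or shortened because only about 15 controls are expected. Claim no power gain.
3. **Aim 2 Hypothesis 2.** Apply the same adjustment or justify leaving it out. That test also names no adjusters, and Section 8.3.5 lists RANKL and OPG as varying with age. Its predictors are changes rather than levels, but the documents do not show that changes are unrelated to age.
4. **Fractures.** Exclude only marker samples taken after a fracture. Add a sensitivity analysis with all samples by randomised group, reporting how many controls began off-study pamidronate after a fracture (Section 7.7).

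**Cost.** The change is to wording only; every covariate is already scheduled. With 30 controls and Tanner stage and race as single terms, five adjusters leave 30 − 2 − 5 = 23 residual degrees of freedom. The partial correlation detectable with 80% power rises from tanh(2.80/√27) = 0.49 to tanh(2.80/√22) = 0.54. With 15 pQCT controls it rises from 0.67 to 0.71 with age and sex (11 df), or to 0.76 with four adjusters (9 df). Dropping only post-fracture samples still leaves some selection, hence the all-samples sensitivity analysis.
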